## SYNOPSIS

Protocol Title:	A Single-Center, Randomized, Double Masked, Placebo Controlled Clinical Study to Assess the Safety and Efficacy of TOP1630 Ophthalmic Solution Compared to Placebo in Subjects with Dry Eye Syndrome
Protocol Number:	TOP1630-TV-04
Study Drug:	1) 0.01% TOP1630 Ophthalmic Solution 2) 0.1% TOP1630 Ophthalmic Solution 3) Placebo (Vehicle solution with no TOP1630)
Study Phase:	2
Study Objective:	In subjects with dry eye syndrome: The primary objective of this study is to compare the safety and tolerability of TOP1630 Ophthalmic Solution to placebo. The secondary objectives are to compare the efficacy of TOP1630 Ophthalmic Solution to placebo for the treatment of the signs and symptoms of dry eye syndrome.
Overall Study Design	
Structure:	Double-masked, randomized, single-center study
Duration:	An individual subject's participation time for the Comfort Assessment is expected to be approximately 12 days. An individual subject's participation in the Safety and Efficacy Assessment is expected to be approximately 5 weeks (35 days).
Controls:	Placebo Ophthalmic Solution (Vehicle)
Dosage/Dose Regimen:	For the Comfort Assessment, 8 eligible subjects will be randomized to either active drug (TOP1630) or placebo (in the ratio of 3 active: 1 placebo) and the same subjects will be cycled through each dose cohort as described below unless a study stopping criterion is met in which case a lower dose regimen may be used for subsequent cohorts:  Placebo or 0.01% TOP1630 bilaterally TID at Visit 1, followed by a rest day, followed by a day with a single dose of placebo or 0.1% TOP1630 bilaterally, followed by a rest day, and then a day of TID dosing with placebo or 0.1% TOP1630 bilaterally, followed

	
by a rest day. Unless stopping criteria are implemented, subjects will proceed to receiving 4 consecutive days dosing of placebo or 0.1% TOP1630 TID (as described in Summary of Visit Schedule).
 
For the Safety and Efficacy Assessment, eligible subjects will be randomized to one of the treatments below (in the ratio of 1 active: 1 placebo) to be administered bilaterally TID for 28 days (from Visit 2b to Visit 4b).
 
1) TOP1630 Ophthalmic Solution 2) Placebo (Vehicle with no TOP1630)
 
TOP1630 dose selection will be based upon the evaluation of emergent (blinded) data from the Comfort Assessment and will not exceed the highest dose tested in that part of the study.
 
During a 7 day study run-in period prior to randomization, all subjects will receive Placebo Ophthalmic Solution (Vehicle) bilaterally at the same dosing frequency as TOP1630.

Summary of Visit Schedule:	
Comfort Assessment 8 visits over the course of 12 days Visit 1a = Day 1, 0.01% TOP1630 or Placebo TID; Comfort Assessment Visit 2a = Day 2, Physician Assessment Visit 3a = Day 3, 0.1 % TOP1630 or Placebo QD, Comfort Assessment Visit 4a = Day 4, Physician Assessment Visit 5a = Day 5, 0.1 % TOP1630 or Placebo TID; Comfort Assessment Visit 6a = Day 6, Physician Assessment Visit 7a = Day 8, 0.1% TOP1630 or Placebo TID, Comfort Assessment followed by dosing daily with 0.1% TOP1630 or Placebo TID at home for Day 9 , Day 10 and Day 11 Visit 8a = Day 12, Physician Assessment
 
Safety and Efficacy Assessment 4 visits over the course of approximately 5 weeks Visit 1b = Day <math>-7 \pm 1</math> day, CAE Screening Visit 2b = Day 1, CAE Confirmation / Baseline

	
Visit 3b = Day <math>15 \pm 1</math> day, 2-Week Follow-Up / CAE Test
 
Visit 4b = Day <math>29 \pm 2</math> days, 4-Week Follow-Up / CAE Test / Exit

Measures Taken to Reduce Bias:	This is a randomized treatment assignment, double masked study.
Study Population Characteristics	
Number of Subjects:	
Total 68
 
6 active and 2 placebo in the Comfort Assessment
 
30 active and 30 placebo in the Safety and Efficacy Assessment

Condition/Disease:	Dry Eye Syndrome
Inclusion Criteria:	
Subjects must meet all of the following requirements to be eligible for enrollment into the study. Subjects who participate in the Comfort Assessment will not be permitted to participate in the Safety and Efficacy Assessment.
 
For the Comfort Assessment:
 
 
1) Be at least 18 years of age;
 
2) Provide written informed consent;
 
3) Have a patient reported history of dry eye for at least 6 months prior to Visit 1a;
 
4) Have a history of use or desire to use eye drops for dry eye symptoms for at least 6 months prior to Visit 1a;
 
 
For the Safety and Efficacy Assessment:
 
All of the above criteria (at Visit 1b), and:
 
 
5) Report a score of <math>\geq 2</math> in at least one symptom of the Ora Calibra® Ocular Discomfort & 4-Symptom Questionnaire at Visits 1b and 2b;
 
6) Report an OSDI score <math>\geq 18</math> at Visits 1b and 2b;
 
7) Have a conjunctival redness score of <math>\geq 1</math> according to the Ora Calibra® scale in at least one eye at Visits 1b and 2b;
 
8) Have a tear film break-up time (TFBUT) <math>>1</math> and <math>< 7</math> seconds in at least one eye at Visit 1b and 2b;
 
9) Have a Schirmer's Test score of <math>\leq 10</math> mm and <math>\geq 1</math> mm in at least one eye at Visits 1b and 2b;
 
10) Have a corneal fluorescein staining score of <math>\geq 2</math>
 

	
according to the Ora Calibra® scale in at least one region (e.g. inferior, superior, or central) in at least one eye at Visits 1b and 2b;
 
11) Have a total lissamine green conjunctival score of <math>\geq 2</math>, based on the sum of the temporal and nasal regions of the conjunctiva according to the Ora Calibra® scale in at least one eye at Visits 1b and 2b;
 
12) Demonstrate a response to the CAE® at Visits 1b and 2b as defined by:
 

Having at least a <math>\geq 1</math> point increase in fluorescein staining in the inferior region in at least one eye following CAE exposure on the Ora Calibra® scale; and

Reporting an Ocular Discomfort score <math>\geq 3</math> at 2 or more consecutive time points in at least one eye during CAE exposure on the Ora Calibra® scale (if a subject has an Ocular Discomfort rating of 3 at time = 0 for an eye, s/he must report an Ocular Discomfort rating of 4 for two consecutive measurements for that eye).

 
13) Have at least one eye (the same eye) satisfy all criteria for 7, 8, 9, 10, 11, and 12 above;
 
14) At Visit 2b, subjects must have at least 5 days' worth of diary symptom data and deemed by the PI to be at least 80% compliant with vehicle eye drops.

Exclusion Criteria:	
Subjects may not participate in the study (Comfort Assessment as well as the Safety and Efficacy Assessment) if any of the following criteria are met:
 

1) Unable or unwilling to follow instructions, including participation in all study assessments and visits;

2) Have any clinically significant slit lamp findings at Visit 1(1a or 1b) that may include active blepharitis, meibomian gland dysfunction (MGD), lid margin inflammation or active ocular allergies that require therapeutic treatment, and/or in the opinion of the investigator may interfere with study parameters;

3) Be diagnosed with an ongoing ocular infection (bacterial, viral, or fungal), or active ocular inflammation at Visit 1 (1a or 1b);

4) Have any significant ocular lesion that could

	
interfere with assessment of safety or efficacy or prevent study conduct in the opinion of the PI;
 

5) Have worn contact lenses within 14 days of Visit 1 (1a or 1b) or anticipate using contact lenses during the study;

6) Have used any eye drops within 2 hours of Visit 1 (1a or 1b);

7) Have previously had laser-assisted in situ keratomileusis (LASIK) surgery within the last 12 months or any other ocular surgeries within the last 6 months;

8) Have used Restasis® or Xiidra™ within 90 days of Visit 1 (1a or 1b);

9) Have used topical ocular steroids within 30 days of Visit 1 (1a or 1b);

10) Have any planned ocular and/or lid surgeries over the study period;

11) Have temporary punctal plugs at Visit 1 that have not been stable within 45 days of Visit 1 (1a or 1b) or anticipate having temporary punctal plugs inserted during the study;

12) Have had punctal occlusion (not including punctal plugs) within 6 months of Visit 1(1a or 1b);

13) Be currently taking any topical ophthalmic prescription (including medications for glaucoma) or over-the-counter (OTC) solutions, artificial tears, gels or scrubs, and cannot discontinue these medications for the duration of the trial (excluding medications allowed for the conduct of the study) or have used any of these medications in the previous 24 hours prior to visit 1 (1a or 1b);

14) Have corrected visual acuity greater than or equal to logMAR+0.7 as assessed by Early Treatment of Diabetic Retinopathy Study (ETDRS) scale in both eyes at Visit 1 (1a or 1b);

15) Have an uncontrolled systemic disease;

16) Be a woman who is pregnant, nursing or planning a pregnancy;

17) Be unwilling to submit a urine pregnancy test at Visit 1 (1a or 1b) and Visit 8a or 4b) (or early termination visit) if of childbearing potential. Non-childbearing potential is defined as a woman who is permanently sterilized (e.g. has

--	---

	
had a hysterectomy or tubal ligation), or is post-menopausal (without menses for 12 consecutive months);
 
18) Be a woman of childbearing potential who is not using an acceptable means of birth control; acceptable methods of contraception include: hormonal – oral, implantable, injectable, or transdermal contraceptives; mechanical – spermicide in conjunction with a barrier such as a diaphragm or condom; IUD; or surgical sterilization of partner. For non-sexually active females, abstinence may be regarded as an adequate method of birth control; however, if the subject becomes sexually active during the study, she must agree to use adequate birth control as defined above for the remainder of the study;
 
19) Have a known allergy and/or sensitivity to the test article or its components;
 
20) Have a condition or be in a situation which the investigator feels may put the subject at significant risk, may confound the study results, or may interfere significantly with the subject's participation in the study;
 
21) Be currently enrolled in an investigational drug or device study or have used an investigational drug or device within 30 days of Visit 1 (1a or 1b). Subjects that were enrolled in the Comfort Assessment will be excluded from participating in the Safety and Efficacy Assessment;
 
22) Be currently using any medication known to cause ocular drying that is not used on a stable dosing regimen for at least 30 days prior to Visit 1 (1a or 1b); antihistamines are not allowed at any time during the study.

Study Formulations:	

• 0.01% TOP1630 Ophthalmic Solution

• 0.1% TOP1630 Ophthalmic Solution

• Placebo (Vehicle minus active)

Evaluation Criteria	

Safety Measures:	
For the Comfort Assessment:
 

• Visual acuity (ETDRS)

• Slit-lamp biomicroscopy

• Adverse event query

• Vital Signs

• Drop Comfort Assessment

• Intraocular pressure (non-contact) at all Visits.

 
For the Safety and Efficacy Assessment:
 

• Visual acuity (ETDRS)

• Slit-lamp biomicroscopy

• Corneal Sensitivity

• Adverse event query

• Undilated Fundoscopy

• Vital Signs

• Drop Comfort Assessment

• Intraocular pressure (non-contact)

 
Stopping criteria will be utilized in the Comfort Assessment to ensure that an appropriate dose can be carried forward into the Safety and Efficacy Assessment. This may include use of a lower dose regimen in the multiple dose assessment of comfort. Stopping criteria will also be utilized during the conduct of the Safety and Efficacy Assessment.

Exploratory Efficacy Measures:	

• Corneal fluorescein staining using the Ora Calibra® Scale and NEI Scale

• Conjunctival lissamine green staining using the Ora Calibra® Scale and NEI Scale

• Visual Analogue Scale (VAS) for symptoms (Pre-CAE®)

• Tear film break-up time (TFBUT)

• Conjunctival redness the Ora Calibra® scale

• Schirmer Test at Visits 2b, 3b, and 4b

• Ora Calibra® Ocular Discomfort & 4-Symptom Questionnaire

• OSDI®

• Ora Calibra® Lid Margin Redness

• Ora Calibra® Posterior Lid Edge Evaluation

• OPI 2.0

• Ora Calibra® Ocular Discomfort Scale

Other:	Biomarker assessment by Impression Cytology (OPIA Eyeprim™)

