### **Exclusion Criteria**

Subjects may not participate in the study (Comfort Assessment as well as the Safety and Efficacy Assessment) if any of the following criteria are met:

1. Unable or unwilling to follow instructions, including participation in all study assessments and visits;
2. Have any clinically significant slit lamp findings at Visit 1 (1a or 1b) that may include active blepharitis, meibomian gland dysfunction (MGD), lid margin inflammation or active ocular allergies that require therapeutic treatment, and/or in the opinion of the investigator may interfere with study parameters;
3. Be diagnosed with an ongoing ocular infection (bacterial, viral, or fungal), or active ocular inflammation at Visit 1 (1a or 1b);
4. Have any significant ocular lesion that could interfere with assessment of safety or efficacy or prevent study conduct in the opinion of the PI;
5. Have worn contact lenses within 14 days of Visit 1 (1a or 1b) or anticipate using contact lenses during the study;
6. Have used any eye drops within 2 hours of Visit 1 (1a or 1b);
7. Have previously had laser-assisted *in situ* keratomileusis (LASIK) surgery within the last 12 months or any other ocular surgeries within the last 6 months;
8. Have used Restasis® or Xiidra™ within 90 days of Visit 1 (1a or 1b);
9. Have used topical ocular steroids within 30 days of Visit 1 (1a or 1b);
10. Have any planned ocular and/or lid surgeries over the study period;
11. Have temporary punctal plugs at Visit 1 that have not been stable within 45 days of Visit 1 (1a or 1b) or anticipate having temporary punctal plugs inserted during the study;
12. Have had punctal occlusion (not including punctal plugs) within 6 months of Visit 1(1a or 1b);
13. Be currently taking any topical ophthalmic prescription (including medications for glaucoma) or over-the-counter (OTC) solutions, artificial tears, gels or scrubs, and cannot discontinue these medications for the duration of the trial (excluding medications allowed for the conduct of the study) or have used any of these medications in the previous 24 hours prior to visit 1 (1a or 1b);
14. Have corrected visual acuity greater than or equal to logMAR+0.7 as assessed by Early Treatment of Diabetic Retinopathy Study (ETDRS) scale in both eyes at Visit 1 (1a or 1b);
15. Have an uncontrolled systemic disease;
16. Be a woman who is pregnant, nursing or planning a pregnancy;

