### **5.3 Withdrawal Criteria and Study Stopping Criteria**

Subjects may withdraw consent from study participation at any time.

If at any time during the study the investigator determines that a subject's safety is or has been compromised, the subject may be withdrawn from the study.

Subjects may be discontinued prior to their completion of the study due to the following safety stopping criteria being met for any subject:

- Persistent loss of 3 or more lines of visual acuity not explained by the condition under investigation and confirmed upon repeat testing
- Development of persistent corneal opacities or severe keratitis
- Persistent ocular irritation or redness not explained by condition
- IOP increase of 12 or more confirmed upon repeat testing
- Sight threatening adverse events such as corneal melting or corneal ulceration;
- Any other possibly related adverse events

Other reasons for discontinuation:

- Protocol violations

- Administrative reasons (e.g., inability to continue, lost to follow up)
- Subject choice (e.g. withdrawal of consent)
- Non compliance
- Any valid medical reason at discretion of investigator (see section 8.6.2)
- Other

Notification of a subject discontinuation and the reason for discontinuation will be made to Ora and/or study Sponsor and will be clearly documented in the eCRF.

Discontinued subjects will not be replaced.

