## 8 STUDY METHODS AND PROCEDURES

### 8.1 Subject Entry Procedures

#### 8.1.1 Informed Consent

Prior to a subject's participation in the trial (i.e., prior to changes in a subject's medical treatment and/or prior to study related procedures), the study will be discussed with each subject, and subjects wishing to participate must give written informed consent using an informed consent form (ICF). The informed consent form must be the most recent version that has received approval/favorable review by a properly constituted Institutional Review Board (IRB).

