#### 8.1.2 Washout Intervals

Prohibited medications, treatments, and activities are outlined in the Exclusion Criteria (Section 5.2).

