## Visit 4b (Day 29 ± 2): 4-Week Follow-Up and Study Exit

### Pre-CAE® Procedures

- Collection and review of study drug and subject diaries
- Subject will be asked if he/she dosed with study drug on the morning of the visit; if the subject indicates he/she dosed that morning, he/she should wait at least 4 hours from the time of dosing before efficacy assessments are performed
- Medical / medication history update
- Adverse event query
- Ora Calibra® Ocular Discomfort
- Ora Calibra® Ocular Discomfort & 4-Symptom Questionnaire
- OSDI®
- 7 question Visual Analogue Scale (VAS) for symptoms of DES
- Visual Acuity
- Vital Signs
- Urine pregnancy test (for females of childbearing potential)
- Slit-lamp Biomicroscopy
- Ora Calibra® Conjunctival Redness
- Ora Calibra® Lid Margin Redness
- Ora Calibra® Posterior Lid Edge Evaluation
- Ora Calibra® OPI 2.0
- TFBUT
- Fluorescein staining – Ora Calibra® and NEI scale
- Lissamine Green staining – Ora Calibra® and NEI scale
- Corneal Sensitivity
- Unanesthetized Schirmer's Test, to be performed at least 15 minutes after Lissamine Green staining
- 90-minute CAE® exposure;
  - Ora Calibra® Ocular Discomfort upon entering the CAE® and every 5 minutes thereafter;

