14.6 Intraocular Pressure (IOP)

IOP will be measured at Visits 1b (post-CAE®) and 4b (post-CAE®). IOP will be summarized for both eyes combined by visit and treatment group using quantitative summary statistics. At Visit 4b, an IOP of ≥ 21 mmHg AND ≥ 10 mmHg over baseline (Visit 1b) will be considered an AE, and presented in the tabular summary. Results will be listed for both eyes at each visit.

15. Tolerability Analyses

Two tools will be used to assess drop comfort, each of which will be assessed at Visit 2b (Day 1) and Visit 3b (Day 15 ± 1), following the first dose of study drug.

subject will be used for this analysis. Drop comfort will be summarized using quantitative summary statistics. Statistical comparisons will employ two-sample *t*-tests as the primary method of analysis.

- Ora Calibra® Drop Comfort Questionnaire will be used to assess drop comfort

Drop Comfort Questionnaire responses will be summarized using qualitative summary statistics. Subjects with at least one negative response will also be summarized.

16. Exploratory Efficacy Analyses

The continuous and ordinal secondary efficacy variables collected at each visit will be summarized descriptively (n, mean, SD, median, minimum and maximum), and analyzed with two-sample *t*-tests comparing the active treatment groups to placebo. All visit-based data will be analyzed at each visit as well as change from baseline. A Wilcoxon rank sum test and an ANCOVA model adjusting for baseline will also be assessed where appropriate. Corneal fluorescein staining by region and total (Ora and NEI scales), lissamine green staining by region, TFBUT, conjunctival redness, unanesthetized Schirmer's test, ocular symptoms (Ora Calibra® scales and VAS), OSDI®, ocular discomfort and changes from baseline in these measures will be analyzed by visit and time point, where applicable (i.e., pre- and post-

[figure not shown]
CAE[®]), using two-sample *t*-tests and Wilcoxon rank sum tests. Changes from baseline will also be analyzed using ANCOVA models adjusting for baseline values. For the measures of symptoms during CAE[®], the ANCOVA models will also include the pre-CAE[®] measure as a covariate. Symptoms recorded on the daily diary will be analyzed using repeated measure ANCOVA models, where baseline scores are calculated as the average scores in the run-in period and post-baseline scores are calculated as weekly morning, afternoon, evening, and daily averages.

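### Exclusion 13 gives glaucoma drops the same 24-hour rule as artificial tears, so a patient who has lapsed from them is not excluded by rule and could go about 5 weeks untreated between scheduled IOP readings

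*Protocol*

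**What the plan says.** Exclusion 13 reads the same in the protocol Synopsis and in Section 5.2. Its first limb covers people who would "Be currently taking any topical ophthalmic prescription (including medications for glaucoma) or over-the-counter (OTC) solutions, artificial tears, gels or scrubs, and cannot discontinue" these products for the length of the trial. Its second limb covers use of any of them "in the previous 24 hours prior to visit 1 (1a or 1b". Section 8.1.2, on washout, adds nothing further: "Prohibited medications, treatments, and activities are outlined in the Exclusion Criteria (Section 5.2".

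Elsewhere the same list sets longer washouts: 90 days for Restasis or Xiidra (Exclusion 8) and 30 days for topical steroids (Exclusion 9). No criterion refers to glaucoma as a diagnosis, to ocular hypertension or to an IOP level.

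Section 8.2.1 carries the exclusion list forward as the treatments disallowed during the study, and Section 8.2.2 allows no escape medication.

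For the 4-week part, SAP 14.6 states: "IOP will be measured at Visits 1b (post-CAE®) and 4b (post-CAE". The visit lists in protocol Section 8.3.1 and Table 2 of Appendix 1 agree. Visit 4b is titled "4-Week Follow-Up and Study Exit". In the Comfort Assessment, by contrast, IOP is read at all 8 visits.

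**The concern.** Stopping an artificial tear and stopping a pressure-lowering drop are different decisions. The first may cost comfort; the second removes treatment for a condition that can progress without symptoms. The criterion names glaucoma drugs and then handles both kinds of product alike.

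As written, someone who has been prescribed such drops but has let them lapse for a day can pass Exclusion 13 if judged able to do without them. Once enrolled, that person is not meant to resume them. No pressure reading is scheduled between Visit 1b and the last day of participation. What is at stake is an avoidable risk to an individual subject, in a first-in-man study whose primary objective is safety and tolerability.

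**Working it through.** **Step 1: does the wording let such a person through?** The sentence joins its conditions with one 'and' and one 'or', so it can be parsed in two ways:

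- Reading A: (current user and cannot discontinue) or used within 24 hours.
- Reading B: current user and (cannot discontinue or used within 24 hours).

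| Person | Excluded under A | Excluded under B |
|---|---|---|
| Current user, cannot discontinue | yes | yes |
| Current user, can discontinue, used within 24 h | yes | yes |
| Counted as current user, can discontinue, none within 24 h | no | no |
| Lapsed and not counted as current, can discontinue, none within 24 h | no | no |

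The last two rows are the people at issue. Neither reading excludes them.

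**Step 2: how long between scheduled IOP readings?** Inputs from protocol Section 8.3.1: Visit 1b on Day -7 ± 1, Visit 2b on Day 1, Visit 4b on Day 29 ± 2. With no Day 0:

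- Planned: 7 + 28 = 35 days, which reproduces the participation time in protocol Section 8.8.
- Shortest: (7 - 1) + (28 - 2) = 32 days.
- Longest: (7 + 1) + (28 + 2) = 38 days.

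Counting a Day 0 would add one day to each. Scheduled IOP readings at Visits 2b and 3b: none.

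**Step 3: minimum time off drops by exit.** Someone who just clears the 24-hour limb has been off for 1 day at Visit 1b, and so for 1 + 35 = 36 days (33 to 39) at Visit 4b.

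**Step 4: who can reach this position?** Section 8.1.1 requires consent "prior to changes in a subject's medical treatment and/or prior to study related procedures", and Section 8.3.1 lists consent as a Visit 1b procedure. A site should therefore not ask a treated patient to stop before Visit 1b, and a patient who has not stopped fails the 24-hour limb. What remains is mainly people who had already stopped or missed doses for their own reasons.

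**Step 5: price of a stricter rule.** Section 5.1 expects about 150 screened for about 60 randomized: 150 / 60 = 2.5 screenings per randomized place. The stated 60% screen-failure rate gives the same figure: 1 / (1 - 0.60) = 2.5.

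**The case against.** The case for leaving the text alone is substantial.

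- **The natural reading.** A patient who needs pressure control is one who cannot discontinue, and that may be why glaucoma drugs are named. Exclusion 20 lets the investigator keep out anyone at significant risk. This protocol relies on judged eligibility elsewhere (Exclusions 2 and 4), so wanting a bright line is partly preference. This stands as a reason to expect few cases, but it leaves the outcome to judgment.
- **The route is narrow.** The 24-hour limb and the consent rule remove current daily users almost entirely. This stands, and it limits the point to people who have lapsed or stopped.
- **Other safeguards.** At Visit 1b, IOP and fundoscopy are listed before the post-CAE qualification review, although no IOP limit applies there. Visits 2b and 3b include medication updates, visual acuity, slit-lamp examination and adverse event queries. Section 8.4.2 permits IOP at an unscheduled visit. If safety is compromised, Section 5.3 says "the subject may be withdrawn from the study". These are real safety contacts, but none is a scheduled pressure reading.
- **A look-back alone is a poor remedy.** A 30-day look-back would not stop anyone from coming off treatment to qualify. It would raise minimum time off drops by exit from 36 days to 30 + 35 = 65 days (62 to 68), and it adds no monitoring. This objection succeeds, which is why the criterion below also turns on being currently prescribed the drop.

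A reader might also infer that residual drug effect lowers the Visit 1b IOP baseline and so distorts the safety comparison. The documents do not support this. They give neither the number of such subjects, nor the size of a drop's effect, nor how much of it remains after a day.

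**Conclusion.** The point holds as a small patient-safety improvement. Exclusion 13 does not exclude by rule a person prescribed pressure-lowering drops who has been off them for 24 hours and is judged able to stop. In the 4-week part that person would be untreated for the 35 days (32 to 38) between the only two scheduled IOP readings. The number affected is not given and is probably few or none. No estimate, test, analysis population or stated probability depends on it, and no mmHg figure should be attached to it. The Comfort Assessment is much less exposed.

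Two stronger conclusions should not be drawn. The first is that the protocol invites sites to take glaucoma patients off treatment; the consent requirement and the 24-hour limb point the other way. The second is that Exclusion 13 is what leaves the Section 5.3 criterion, "IOP increase of 12 or more confirmed upon repeat testing", without a scheduled reading before exit. That gap applies to every subject in the 4-week part. It is a separate issue, and rewording the exclusion does not address it.

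The conclusion on wording and schedule rests on the text alone. The judgment that few subjects are affected assumes that sites follow the consent rule and use Exclusion 20 sensibly.

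**What to change.** In both the Synopsis and Section 5.2, take the mention of glaucoma drugs out of Exclusion 13 and add a separate criterion: *Be currently prescribed, or have used within 30 days of Visit 1 (1a or 1b), any glaucoma or other intraocular-pressure-lowering eye drop.*

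The words 'currently prescribed' carry the weight: a patient cannot then become eligible merely by stopping. The 30 days follows the form of Exclusion 9 and is a starting value for the medical team to confirm. Because the new criterion sits in Section 5.2, the cross-references in Sections 8.1.2 and 8.2.1 pick it up unchanged.

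The cost is one criterion reworded and one added, in two places, with no new visit, measurement or SAP text. There may be a few more screen failures, at about 2.5 screenings for each randomized place closed.
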